	Usual care will consist of any treatment(s) (including no treatment) other than andexanet administered within 3 hours post-randomization that the Investigator and/or other treating physicians consider to be appropriate. For andexanet treatment, patients will receive one of two dosing regimens of andexanet based on which FXa inhibitor they received and the amount and timing of the most recent dose. Andexanet will be given via an intravenous (IV) bolus administered over ~15 minutes (low dose) to 30 minutes (high dose) followed immediately by a continuous infusion administered over ~120 minutes. There will be no cross-over between treatment groups.
	It is intended that all patients initiate treatment as soon as possible after the treatment allocation is known. For: 1) anti-fXa activity; and 2) diagnostic evaluations to support hemostatic efficacy (i.e., imaging tests, National Institutes of Health Stroke Scale [NIHSS]), baseline is defined as the most recent assessment within 15 minutes and 120 minutes prior to randomization, respectively. For post-baseline efficacy assessments, time 0 is defined as randomization.
	AEs including serious AEs (SAEs) and TEs, and survival will be followed through the Day 30 post-treatment visit for all patients (or to day 120 if applicable). The study Schedule of Activities can be found in Appendix A.
	The primary efficacy endpoint will be adjudicated based on data collected through 12 hours post-randomization. The following data are planned to be captured: imaging and clinical elements (brain Magnetic Resonance Imaging [MRI] or Computed Tomography [CT]), assessment using the National Institutes of Health Stroke Scale (NIHSS) performed by a person blinded to treatment allocation (Appendix E), and concomitant medication entry and hospital records for rescue therapy.

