7.2. Concomitant Medications, Hemostatic, and Pro-coagulant Treatments

The use of concomitant medications and treatments, including surgeries, is summarized in Table 5 and detailed in the subsections below.

Concomitant Medication and Treatments	Allowed Use
Anticoagulants (e.g., direct thrombin inhibitors, FXa inhibitors, vitamin-K antagonists) and Antiplatelet Drugs (e.g., prasugrel, ticagrelor, clopidogrel, aspirin, NSAIDs)	• For both treatment groups, can be restarted at any time based on clinical judgment.
Platelets and PRBCs	• Patients in both groups may receive platelets and/or PRBC transfusions at any time.
	• Use of platelets or red blood cells will not have any bearing on hemostatic efficacy.
Pro-Coagulant Blood Products (pro- coagulant factor infusions [e.g., 3- or 4-factor PCC/activated PCC, recombinant fVIIa, plasma, FFP, FEIBA [®]], and whole	• For patients randomized to usual care treatment, blood products may be administered within the initial 3-hour treatment window post-randomization per institutional/local practices and/or guidelines.
blood)	• For patients randomized to and exanet, blood products may be administered if a patient is found to have hematoma expansion.
	• For both treatment groups, administration of blood products between 3 hours post-randomization and the 12-hour hemostatic efficacy evaluation will result in the patient being considered to have poor/none hemostatic efficacy.

 Table 5:
 Allowed Use of Concomitant Medications and Treatments

Concomitant Medication and Treatments	nts Allowed Use		
	• Misadministration of procoagulant blood products contrary to treatment allocation within 3 hours post-randomization (including and exanet in usual care arm) will be reviewed by EAC.		

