7.2.1. Anticoagulants and Antiplatelet Drugs

Investigators may choose to re-start anticoagulants or antiplatelet drugs (including, but not limited to prasugrel, ticagrelor, clopidogrel, aspirin, and Non-Steroidal Anti-Inflammatory Drugs [NSAIDs]) at any time based on clinical judgment. If anticoagulants or antiplatelet agents are restarted during the study, the date, time, and agent(s) used should be recorded on the CRFs.

7.2.2. Blood Products

To maintain uniformity in transfusion practices across study participants, it is strongly suggested that the trigger for PRBC transfusion is a hemoglobin $\leq 8.0 \text{ g/dL} (\pm 1 \text{ g/dL})$. The hemoglobin triggering a transfusion, clinical stability factors (e.g., shock) influencing the decision to transfuse, as well as number of units transfused should be recorded on the CRFs.

For both treatment groups, transfusion of platelets and/or PRBCs may be performed at any time without any bearing on the primary efficacy endpoint.

Use and timing of blood products, including number of units transfused and the date and time of administration should be recorded on the CRFs.

7.2.3. Procoagulant Blood Products

For patients randomized to usual care treatment, pro-coagulant factor infusions (e.g., 3- or 4-factor PCC/activated PCC, rfVIIa, plasma, FFP, FEIBA[®]), and/or whole blood may be administered within the initial 3-hour treatment window post-randomization according to standard institutional/local practices and/or guidelines. If a patient is randomized to andexanet, Investigators may consider using pro-coagulant factor infusions, as listed above, if a patient is found to have hematoma expansion (i.e., a > 35% increase in volume from baseline) on either a protocol-driven or clinically-indicated scan. Otherwise, treatment with the above products is strongly discouraged, though not prohibited, during the entire 30-day observation period.

For both treatment groups, use of pro-coagulant factor infusions (e.g., 3- or 4-factor PCC/activated PCC, rfVIIa, plasma, FFP, FEIBA[®]) and/or whole blood between 3 hours after randomization and the 12-hour hemostatic efficacy evaluation measurements will result in the patient being considered to have poor/none hemostatic efficacy.

Misadministration of procoagulant blood products contrary to treatment allocation within 3 hours post-randomization (including and exanet in usual care arm) will be reviewed by EAC.

7.2.4. Hemostatic Agents

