7.4. Continued Bleeding, Re-bleeding, and Rescue Therapy

In this study, there is potential for patients to experience continued bleeding and/or re-bleeding after therapy (be it usual care or andexanet). That said, because they represent the two potential mechanisms for hematoma expansion, continuous bleeding and re-bleeding should be considered within the broader scope of hematoma expansion. That is, patients with continuous bleeding and patients with re-bleeding represent subsets of patients with hematoma expansion. Therefore, when considering the use of rescue therapy for continued bleeding or re-bleeding, Investigators should consider whether the patient has evidence of hematoma expansion (defined as any increase from baseline in hematoma volume greater than 35%).

For all patients, while Investigators are strongly encouraged to perform diagnostic imaging if continued or recurrent bleeding is suspected, any therapy (other than andexanet) may be used at any time to address continued or recurrent bleeding. No andexanet dosing (for the usual care group) or re-dosing (for the andexanet group) is allowed.

For all patients, any blood product (excluding PRBCs and platelets), pro-coagulant factor infusions, or systemic hemostatic therapy (except tranexamic acid) specifically intended to address continued or recurrent bleeding (as listed in Section 7.2.2 and Section 7.2.4), initiated at least 3 hours after randomization but before the 12-hour hemostatic efficacy assessment, will be considered rescue therapy. Any patient receiving such systemic rescue therapy will be considered a treatment failure (i.e., poor/none hemostatic efficacy).

Additionally, any unplanned rescue surgical procedure specifically intended to treat the hematoma at any time between 3 hours post-randomization and the 12-hour hemostatic efficacy evaluation measurements will result in the patient being considered to have poor/none hemostatic efficacy.

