	• These cases will be further adjudicated to determine if they are non-evaluable from administrative reasons (e.g., scan not available for technical reason, transfer to another facility, or hematoma drainage not due to clinical deterioration) or clinical reasons (scan not available because of patient deterioration). Cases assessed as non-evaluable for clinical reasons will be imputed as having poor/none hemostatic efficacy.

Note: This Appendix is intended only as a guide to Investigators and is not intended to be comprehensive. Full details on the rating of hemostatic efficacy are provided in the Adjudication Charter.

^a Rescue therapies defined as any pro-coagulant replacement factor products (e.g., 3- and 4-factor prothrombin complex concentrates, activated PCCs, FEIBA[®], recombinant fVIIa, plasma, FFP, whole blood), any systemic or local hemostatic therapies (except tranexamic acid), or the conduct of unplanned surgeries/procedures to treat the hematoma.

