5.5.6. Rescue Therapy

Rescue therapies include rescue medications and rescue procedures including surgeries. The number of participants receiving rescue therapies (medication or procedures) between 3 and 12 hours post-randomization, as well as the total number of therapies received, will be summarized based on dose of andexanet received (low, high, and total) or the type of UC initially received (PCC, other, no treatment, and total). The CMH test stratified by time from symptom onset to the baseline imaging scan will be used to test the treatment difference in the proportion of participants receiving at least 1 rescue therapy between andexanet and UC. The p-value and 95% CI of the difference in proportion will be presented.

The types of rescue medications used will be tabulated by treatment group; participants reporting > 1 medication within an Anatomical Therapeutic Chemical (ATC) classification or a generic name will be counted only once for that class or name. In addition, the surgeries/procedures used to treat the index hematoma or could impact hematoma volume will be tabulated by treatment group; participants reporting > 1 surgery/procedure will be counted only once for that surgery/procedure.

A by-participant listing of rescue therapies will be provided.

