The majority of cases will not require review by adjudicators as the outcome rating will be obvious based on the core laboratory interpretation, NIHSS scores, and lack of additional treatments or procedures. An algorithm will be applied to the data from the imaging core laboratory and information provided by the sites on CRFs. The algorithm will determine if the case can be immediately classified as excellent, good, or poor/none or whether the case requires review by adjudicators and additional review by the EAC. Cases will be referred for EAC review, if the change in hematoma volume is < 35% and the change in the NIHSS score between baseline and 12 hours is < 7 and if one of the following criteria is met:

- baseline or 12-hour scans (11 to 15 hours post-randomization) missing, uninterpretable, or fall outside the collection window.
- NIHSS scores missing or fall outside the collection window for either baseline or 12-hour evaluations.
- Cases where the blinded imaging core laboratory readers indicate that review by the EAC is needed (or 3 readers disagree on classification of hematoma volume change).
- Cases where the participant was either sedated or intubated for either baseline or 12-hour NIHSS assessment (or both).
- Documented procedures that could potentially drain hematoma between 3- and 12hours post-randomization.
- Cases, where it is determined that there is insufficient information or where it is not otherwise possible to properly assess the effect of treatment, will be further classified by the EAC as follows:
 - Nonevaluable due to administrative reasons (eg, follow-up scans not available/performed/interpretable and the participant transferred to another

facility for administrative purposes); these participants will be analyzed as having poor/none effective hemostasis.

• Nonevaluable due to clinical reasons (eg, the participant died and the participant had unplanned surgery draining hematoma); these participants will be analyzed as having poor/none effective hemostasis.

Identifying Rescue Medications/Procedures

Rescue medications are identified from the concomitant medication CRF pages based on the following:

- 1. If indication for medication is "TO ACHIEVE HEMOSTASIS FOR CONTINUOUS (WORSENING) INTRACEREBRAL HEMORRHAGE BLEED," "TO ACHIEVE HEMOSTASIS FOR INITIAL BLEED," or "TO ACHIEVE HEMOSTASIS FOR NEW BLEED RE-BLEED" (except for tranexamic acid, which is permitted regardless of indication).

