- If the 12-hour NIHSS score is missing or difficult to interpret (eg, discordance with imaging changes, large magnitude changes, or swings in value), the EAC will determine whether the NIHSS score is missing/difficult to interpret due to administrative reasons or clinical reasons.

Cases, where it is determined that there is insufficient information or where it is not otherwise possible to properly assess the effect of treatment, will be further classified by the EAC as "nonevaluable due to administrative reasons" (eg, follow-up scans not available/performed/interpretable and the participant transferred to another facility for administrative purposes) and handled as poor/none in the primary analysis or "nonevaluable due to clinical reasons" (eg, the participant died and the participant had unplanned surgery draining hematoma) and handled as poor/none in the primary analysis.

Handling of Data for Missing Anti-fXa Activity

Values > 950 ng/mL will be replaced with 950 ng/mL (the upper limit of quantitation). Values < 4 ng/mL will be replaced with 4 ng/mL (the lower limit of quantitation). In addition, other values identified as ">", " \geq ", "<", or " \leq " will be replaced with the actual values (eg, > 750 will be replaced with 750). For missing baseline measurements, if any baseline measurement collected outside of visit window is available, then the missing baseline value will be replaced with the out-of-window measurement.

Handling of Data for Thrombin Generation

ETP values identified by the laboratory as below measurement capacity will be replaced with zeros.

Concomitant Medications/Procedure With Partial or Missing Dates

The use of concomitant medications allowed in the study are found in Protocol Section 7.2. Concomitant medications are medications that are started on or after the start of study treatment or are ongoing at the start of study treatment. For participants who are randomized into the UC arm and received no treatment, their randomization date is used as the start of study treatment. If the start date of a medication is partially or completely missing and the end (stop) date and time of the medication does not indicate that it occurred prior to first dose, then the medication will be considered as both prior and concomitant if either type cannot be determined with certainty.

The following imputation rules apply after the above concomitant and prior rules have been followed:

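### SAP 6.1 exempts only tranexamic acid from the rescue-medication rule, so platelets or PRBCs given for the bleed can be scored as failure, contrary to the protocol

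*SAP*

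**What the plan says.** **SAP.** Section 6.1 (Identifying Rescue Medications/Procedures) takes rescue medications from the concomitant-medication CRF pages. An entry qualifies if its indication is one of three hemostasis indications (worsening, initial or new bleed) and its time is >3 to <12 hours after randomization. The one exemption reads "except for tranexamic acid, which is permitted regardless of indication". The Effective Hemostasis part of the same section makes rescue use a treatment failure. An algorithm applied to core-laboratory and CRF data rates most cases without adjudicator review.

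**Protocol.** Platelets and PRBCs are exempt in three places:
- Table 5 (Section 7.2): "Use of platelets or red blood cells will not have any bearing on hemostatic efficacy".
- Section 7.2.2: "transfusion of platelets and/or PRBCs may be performed at any time without any bearing on the primary efficacy endpoint".
- Section 7.4, which defines rescue as "any blood product (excluding PRBCs and platelets"), procoagulant factor infusions, or systemic hemostatic therapy other than tranexamic acid, where these are aimed at continued or recurrent bleeding.

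Appendix B, footnote a, defines rescue by product ("Rescue therapies defined as any pro-coagulant replacement factor products", then hemostatic therapies and procedures) and lists neither platelets nor PRBCs.

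SAP Appendix 5 declares one change from the protocol, to the enrolled set. It declares none to the definition of rescue.

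**The concern.** The protocol has two exemptions from rescue and the SAP rule carries over one. The SAP rule also selects on indication alone, where the protocol selects on product and purpose. A platelet transfusion given to stop the bleed therefore meets every SAP condition while the protocol expressly excludes it.

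Rescue is one of the three components of the primary endpoint, so a wrong flag turns a success into a failure. The additional endpoint in SAP 5.5.6 ("The number of participants receiving rescue therapies (medication or procedures) between 3 and 12 hours post-randomization") depends on the same identification of rescue medication. Treatment is open-label, so equal transfusion use in the two arms is not assured, and the error could favor either arm.

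**Working it through.** **1. The rules applied to one patient.** Platelets at 5 hours, indication recorded as hemostasis for the initial bleed; hematoma volume +10%; NIHSS +1; no other treatment.

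| Step | Protocol | SAP 6.1, read literally |
|---|---|---|
| Volume (no more than 35% growth) | met | met |
| NIHSS (less than +7) | met | met |
| Rescue | no: platelets exempt | yes: indication and time match, not tranexamic acid |
| Rating | excellent (growth no more than 20%) | poor/none |

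**2. Whether the entry would reach the rule.** The rule reads the concomitant-medication pages. Two texts make it plausible that transfusions are there. The protocol synopsis (Study Design) names "concomitant medication entry and hospital records for rescue therapy" among the planned data. SAP 6.1 also states "The use of concomitant medications allowed in the study are found in Protocol Section 7.2", and Table 5 in that section lists platelets and PRBCs. Neither text proves it. PRBCs given only for low hemoglobin carry no hemostasis indication and would not be caught.

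**3. Whether anything visible would correct it.** The EAC-referral list in SAP 6.1 covers scans, NIHSS, reader requests, sedation or intubation, drainage procedures and insufficient information. Transfusion is not on it.

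**4. Size.** Inputs from the documents: success rates 80% (andexanet) and 70% (usual care); 450 per arm; interim at half the sample; two-sided levels 0.0310 and 0.0277. Assumptions, because the documents give no transfusion rate:
- q = share of an arm given platelets or PRBCs for the bleed at >3 to <12 hours and recorded on those pages.
- f = those patients' chance of success otherwise, relative to their arm (1, or 0.5 if they do worse).

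Scored rate = p × (1 − f × q).

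Power is from a two-look bivariate normal calculation: 225 then 450 per arm, pooled-variance test, no dropout.

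*The plan's own figure.* With q = 0 the power is 90.9%, against about 90% stated.

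*Equal use in both arms:*

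| q | Difference, f = 1 | Power, f = 1 | Difference, f = 0.5 | Power, f = 0.5 |
|---|---|---|---|---|
| 0 | 10.0 | 90.9% | 10.0 | 90.9% |
| 1% | 9.9 | 89.8% | 9.95 | 90.3% |
| 3% | 9.7 | 87.3% | 9.85 | 89.2% |
| 5% | 9.5 | 84.7% | 9.75 | 87.9% |

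For example, q = 3% and f = 1: 0.80 × 0.97 − 0.70 × 0.97 = 0.776 − 0.679 = 0.097. Misscored patients: 450 × 0.80 × 0.03 = 10.8 in andexanet and 450 × 0.70 × 0.03 = 9.45 in usual care.

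*Unequal use, 3% against 1%:*
- Higher in andexanet, f = 1: 0.776 − 0.693 = 0.083, a shift of −1.7 points. With f = 0.5: 0.788 − 0.6965 = 0.0915, a shift of −0.85.
- Higher in usual care, f = 1: 0.792 − 0.679 = 0.113, a shift of +1.3 points. With f = 0.5: 0.796 − 0.6895 = 0.1065, a shift of +0.65.

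**The case against.** The strongest reply is that no patient has been shown to be misscored.

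- **Recording.** The Schedule of Activities has a row for blood products and hemostatic treatments separate from the concomitant-medication row, and its footnote 9 limits that row to products used for the intracerebral hemorrhage. Section 7.2.2 asks for transfusion-specific CRF data such as units and the triggering hemoglobin. Both suggest a separate form. The synopsis names a source for rescue therapy, which platelets are not, and Table 5 also covers surgeries, which the SAP reads from another page.
- **Reading.** The SAP is based on Protocol Version 3.0, declares no change to rescue and defers to the Adjudication Charter. It could be read together with the protocol definition. The Charter is not among the documents, and part of the rescue text in SAP Table 3 is lost from the text we have.
- **Scope.** PRBCs would seldom carry a hemostasis indication, which leaves mainly platelets. Every rate used above is assumed.

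These points limit the number of patients affected, possibly to none. They do not remove the conflict. The Schedule row also covers hemostatic treatments, which the SAP rule reads from the concomitant-medication pages, so the row does not establish a separate form. If blood products were all on another form, the rule could miss plasma, PCC and whole blood, which the protocol does count as rescue; the page mapping needs checking in either case. The SAP's pointer to Protocol 7.2 stands under partial and missing dates and does not amend the rescue rule. That rule states its own exception, and a programmer would code that one.

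**Conclusion.** The concern holds: as written, the SAP rule departs from the protocol's definition of rescue within the primary endpoint. With no declared change in Appendix 5, it reads as an incomplete parenthetical rather than an intended revision.

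That the texts conflict is certain. The size of the effect is unknown and depends on transfusions being on the concomitant-medication pages and on assumed rates of use. With equal use of 1% to 5%, the loss is 0.05 to 0.5 points of difference and about 0.6 to 6 points of power. Unequal use of 3% against 1% shifts the difference by 0.65 to 1.7 points, in a direction set by which arm transfuses more. If transfusions are recorded elsewhere, or if the Charter or the lost Table 3 text restores the exemption, scoring is unaffected. It should be fixed, with medium confidence that it matters in practice.

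**What to change.** Before unblinding, extend the parenthetical in SAP 6.1 so that it exempts tranexamic acid, platelets and PRBCs, whatever the recorded indication, and add the matching filter to the program. At the same time, confirm which CRF pages hold transfusions, and that the pages read by the rule include those holding plasma, PCC and whole blood.

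The cost is one SAP phrase, one program filter and one check of the page mapping. Sample size, alpha and patient care do not change; only endpoint scoring is brought back to the protocol's definition.

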- If the 12-hour NIHSS score is missing or difficult to interpret (eg, discordance with imaging changes, large magnitude changes, or swings in value), the EAC will determine whether the NIHSS score is missing/difficult to interpret due to administrative reasons or clinical reasons.

Cases, where it is determined that there is insufficient information or where it is not otherwise possible to properly assess the effect of treatment, will be further classified by the EAC as "nonevaluable due to administrative reasons" (eg, follow-up scans not available/performed/interpretable and the participant transferred to another facility for administrative purposes) and handled as poor/none in the primary analysis or "nonevaluable due to clinical reasons" (eg, the participant died and the participant had unplanned surgery draining hematoma) and handled as poor/none in the primary analysis.

Handling of Data for Missing Anti-fXa Activity

Values > 950 ng/mL will be replaced with 950 ng/mL (the upper limit of quantitation). Values < 4 ng/mL will be replaced with 4 ng/mL (the lower limit of quantitation). In addition, other values identified as ">", " \geq ", "<", or " \leq " will be replaced with the actual values (eg, > 750 will be replaced with 750). For missing baseline measurements, if any baseline measurement collected outside of visit window is available, then the missing baseline value will be replaced with the out-of-window measurement.

Handling of Data for Thrombin Generation

ETP values identified by the laboratory as below measurement capacity will be replaced with zeros.

Concomitant Medications/Procedure With Partial or Missing Dates

The use of concomitant medications allowed in the study are found in Protocol Section 7.2. Concomitant medications are medications that are started on or after the start of study treatment or are ongoing at the start of study treatment. For participants who are randomized into the UC arm and received no treatment, their randomization date is used as the start of study treatment. If the start date of a medication is partially or completely missing and the end (stop) date and time of the medication does not indicate that it occurred prior to first dose, then the medication will be considered as both prior and concomitant if either type cannot be determined with certainty.

The following imputation rules apply after the above concomitant and prior rules have been followed:

- For start date: If the day is missing, then impute with 01, and if both the day and the month are missing, then impute with 01-Jan.
- For end date: If the day is missing, then impute with the last day of that month, and if both the day and the month are missing, then impute with the last visit/contact/survival/death day of study or Day 30.
- If the year is missing, then keep as is. No imputation is required if the complete date is missing.

Definition of Baseline Values

Baseline is defined as the most recent nonmissing assessment within the protocol-defined visit window prior to randomization. If there is no assessment within the visit window of randomization, then the assessment closest to randomization prior to treatment will be used as baseline. Data that are outside the baseline assessment windows specified above will not be excluded from analyses but will be identified as protocol deviations.

Start of Study Treatment

For and exampt treatment group, the start of study treatment will be the start of and exampt. For the UC treatment group, the start of study treatment will be the start of the specific UC drug received by the participant, or if the UC consists of no treatment, then the start of study treatment will be the randomization date for the participant.

Restart of Anticoagulants

The time when anticoagulants were restarted is defined as (date restart anticoagulation - date of the first study treatment) + 1. If the participant is assigned to UC and receive no treatment, then the date of the first study treatment will be replaced by the date of randomization. Oral anticoagulants will be summarized separately.

Study Day

For participants who are randomized to UC group and received no treatment, the study day is calculated based on randomization date. For events prior to randomization, the study day is calculated as date of event - date of randomization; for events on or after randomization, the study day is calculated as date of event - date of randomization + 1. For other participants, the study day is calculated based on the date of treatment initiation, using the same formula as above. Study day is referred as "day" in outputs.

Calculation of On Treatment Nadir

On treatment nadir is the minimum anti-fXa activity post-randomization (ie, value observed at either 1- or 2-hour post-randomization evaluation). A percent reduction will be calculated as the ratio between the maximum reduction from baseline and the baseline value, multiplied by 100.

Length of Hospitalization and Rehospitalization

The following steps will be followed to calculate the length of hospitalization (or rehospitalization):

- The length of stay (LOS) will be calculated as discharge date/time admission date/time + 1.
- If the participant admission time and the discharge time are missing and the dates are the same, the LOS will be assumed to be 1 day.
- If the participant admission time and the discharge time are missing and the dates are not the same, the LOS will be calculated using the date portion of the dates plus 1.
- If the discharge date is missing and there is no new admission date, the date of the 30-day visit or the date of death (whichever is earlier) will be imputed as the discharge date.
- If the participant has withdrawn consent, the discharge date will be imputed as the date of the 30-day visit or the date of death (whichever is earlier and/or available).

Neurologic Deterioration at 24 hours

Neurologic deterioration at 24 hours is defined as an NIHSS increase \geq 4 at 24 hours compared to baseline or a GCS score decrease \geq 2 at 24 hours compared to baseline.

Neurologic Deterioration at 12 hours

Neurologic deterioration at 12 hours is defined as an increase of \geq 7 point from baseline to 12 hours in NIHSS.

Utility-Weighted mRS

Mean utility values will be based on EQ-5D-5L at the same visit and will be determined by averaging the utilities of all participants within each mRS category.

AEs With Partial or Missing Start and End Date

If the start date of an AE is partially or completely missing and the end (stop) date and time of the AE do not indicate that it occurred prior to the first dose, then the determination of treatmentemergent status will be based on the following:

- If the start year is after the year of the first dose, then the AE is treatment emergent.
- If the start year is the same as the year of the first dose and:
 - If the start month is missing, then the AE is treatment emergent.
 - If the start month is present and is the same as or after the month of the first dose, then the AE is treatment emergent.

Page 41 of 52 Alexion Confidential • If the start date is completely missing, then the AE is treatment emergent.

If both start and end dates of AEs are completely missing, no imputation will be performed, and those AEs will be considered treatment emergent.

If the start date is partial:

- 1. If only the day is missing:
 - a. If the month/year of the start date is the same as those of the first study drug administration date, then the missing day will be imputed as the smaller nonmissing value of (day of first study drug administration, day of the AE end date).
 - b. Otherwise, impute the missing day as "01."
- 2. If both day and month are missing:
 - a. If the year of the AE start date coincides with the year of the first study drug administration date, the partial start date will be set as the first study drug date. If this leads to a date after the AE end date, then the missing day and month of the AE start date will be imputed as the day and month of the AE end date.
 - b. If the year of the AE start date is different from the year of the first study drug administration date, the missing day and month of the AE start date will be imputed as "01" and "01."

If the start date of an AE is the same as the first study drug administration date but the time is missing, the AE is treatment-emergent.

If the stop date is partial:

- 1. If only the day is missing:
 - a. The missing day will be imputed as the last of the month, adjusting for the leap year.
- 2. If both day and month are missing:
 - a. If the year of the AE end date coincides with the maximum of (the year of first study drug administration date or the year of the last study drug administration), then the missing month will be imputed as the month of the corresponding study drug administration date (first or last) and the missing day will be imputed as the last of the month adjusting for the leap year.
 - b. Otherwise, the missing day and month of the AE stop date will be imputed as "31" and "12."

Adverse Event of Special Interest (AESI)

The AESI in this study is thrombotic events based on adjudication. The EAC adjudicate TEs or potential TEs based on AE review to include the following: stroke (or cerebral vascular accident), transient ischemic attack, deep vein thrombosis, pulmonary embolism, arterial systemic embolism, and myocardial infarction. For the purposes of adjudication, a "thromboembolic event" is to be considered synonymous with a "TE." Detailed definitions of TEs, as well as AE terms that require adjudication to determine if definitions for a TE are met, are provided in the Adjudication Charter.

Clinically Significant Laboratory Test Abnormalities

Table 5 shows the following clinically significant criteria that will be followed. Additional criteria may be applied.

Laboratory Parameter	Criteria for Clinical Significance
Alkaline phosphatase	\geq 3× ULN
Alanine aminotransferase	\geq 3× ULN
Aspartate aminotransferase	\geq 3× ULN
Bilirubin	\geq 34.2 µmol/L
Blood urea nitrogen	≥ 10.71 mmol/L
Creatinine	\geq 176,8 μ mol/L
Eosinophils/leukocytes	$\geq 10\%$
Hematocrit	Female: $\leq 32\%$ AND $\geq 3\%$ decrease from baseline Male: $\leq 37\%$ AND $\geq 3\%$ decrease from baseline
Hemoglobin	Female: \leq 95 g/L Male: \leq 115 g/L
Neutrophils/leukocytes	≤ 15%
Platelet	$Low: \le 75 \times 10^{9}/L$ High: $\ge 700 \times 10^{9}/L$
Uric acid	Female: \geq 505.59 µmol/L Male: \geq 624.54 µmol/L
Leukocytes	$\begin{split} & \text{Low:} \leq 2.8 \times 10^{9} / \text{L} \\ & \text{High:} \geq 16 \times 10^{9} / \text{L} \end{split}$

Table 5:Clinically Significant Abnormality Criteria

Abbreviation: ULN = upper limit of normal

Clinically Significant Vital Sign Abnormalities

The following clinically significant criteria will be followed:

Table 6: Clinically Significant Vital Sign Criteria

Vital Sign Parameter	Criteria for Clinical Significance
Temperature	< 36.4 °C or > 38.5 °C
Respiratory rate	< 12 or > 40 breaths/min
Heart rate	< 40 or > 160 bpm
Systolic blood pressure	< 70 or > 180 mmHg

Diastolic blood pressure < 40 or > 120 mmHg

Identifying Past Medical History for Select Diagnoses

The following dictionary-derived terms will be used to identify medical history for purposes of the subgroup analyses:

- 1. Atrial fibrillation
- 2. Cardiac failure congestive
- 3. Cerebrovascular accident
- 4. Chronic kidney disease
- 5. Diabetes mellitus
- 6. Hypertension
- 7. Transient ischemic attack/stroke
- 8. Neoplasm malignant
- 9. Deep vein thrombosis
- 10. Thromboembolism
- 11. Pulmonary edema

